5.3 LIFESTYLE CONSIDERATIONS

N/A

5.4 SCREEN FAILURES

Screen failures are defined as participants who consent to participate in this study but are not subsequently assigned to the study intervention or entered in the study. This includes those who fall out during the run in phase prior to randomization. Individuals who do not meet the criteria for participation in this trial (screen failure) because of meeting one or more exclusion criteria that are likely to change over time may be rescreened. Rescreened participants will be assigned the same participant number as for the initial screening.

5.5 STRATEGIES FOR RECRUITMENT AND RETENTION

Setting and Recruitment

We will recruit participants from the 271 primary care clinics within the Wake Forest (WF) Baptist Health System, as well as surrounding providers outside of Atrium Health *in North Carolina*.

Subjects Selection Criteria

See sections 5.1 Inclusion Criteria and 5.2 Exclusions Criteria for details.

See MOP chapter 02 for more Recruitment and Retention information.

6 STUDY INTERVENTION(S) OR EXPERIMENTAL MANIPULATION(S)

6.1 STUDY INTERVENTION(S) OR EXPERIMENTAL MANIPULATION(S) ADMINISTRATION

6.1.1 STUDY INTERVENTION OR EXPERIMENTAL MANIPULATION DESCRIPTION

Web-based Cognitive Behavioral Therapy (web-based CBT). The web-based CBT program is an automated program (i.e., users learn skills with interactive, personalized training without any therapist contact) that includes 8, 35- to 45-minute training sessions, each of which provides an educational rationale and training in cognitive or behavioral pain coping skill drawn from face-to-face CBT³. The sessions and features are controlled by a programming component that applies an “expert systems” approach. That is, it pairs decision rules (in the form of computerized tailoring algorithms) with a knowledge database to simulate the behavior and judgment of an expert – in this case, a highly trained therapist experienced in delivering face-to-face CBT. The decision rules customize (tailor) participants’ experience in the program based on their responses and progress through the program. In other words, our web-based CBT retains the therapeutic components and processes (e.g., knowledge, collaborative skills training, self-monitoring, reinforcement, motivational enhancement, and working alliance) underlying the benefits of the face-to-face interventions on which they are based⁷⁹.

Participants will complete one session per week (on average) over 12 weeks; this timing offers flexibility in completing sessions (e.g., allowing for personal or medical events to delay completion of some

sessions, which we have found users prefer). Session 1 starts with an overview of the CBT program, and the intervention's therapeutic rationale. This overview is followed by training in the first pain coping skill: progressive muscle relaxation. Sessions 2-7 teach, respectively, brief relaxation skills (i.e., "mini-practices"), activity-rest cycling, pleasant activity scheduling, cognitive restructuring ("coping thoughts"), pleasant imagery, and problem solving. Session 8 reviews each skill to consolidate learning and teaches strategies for long-term skill use. Between sessions, participants are asked to practice their newly learned skill and any skills they learned in past sessions. The program also includes a feature to enhance engagement and facilitate practice. This feature is a section of the program that participants access to self-monitor their progress by reviewing and changing practice goals, recording practices and "coping confidence" (self-efficacy for managing pain), viewing graphic summaries of progress over time, and managing automated practice reminders.

Health care professional-delivered MI. The primary purpose of health care professional contact is to enhance participant's motivation to engage in web-based CBT by encouraging participant's continued use and practice of pain coping skills. Subjects randomized to the [duloxetine + web-based CBT] with health care professional support will receive 6 phone calls from MI trained health care professional at week 3, 6, 10, 14, 18 and 22. Telephone sessions may run for 20 minutes on the average. Similar to our previously tested MI protocol to encourage exercise, the MI intervention has 3 phases:

1. First phase: The first two calls will focus on strategies that enhance motivation to practice newly learned pain coping skills. It involves eliciting from the patient statements (i.e. self-motivational statements) that support the following: a) The patient's recognition of the full nature and extent of the problem, b) The patient's concern about how he or she is currently managing the problem, c) The patient's intention of changing in the direction of adaptive pain management, and d) The patient's optimism that changes are possible.
2. Second phase: This phase is devoted to strategies that strengthen commitment to practice newly learned pain coping skills regularly and consistently. Specifically, the third call would include helping the patient develop a plan for change (i.e. shift from why the patient should consider change to how the patient will make changes) communicating free choice, and reviewing consequences of adaptive vs. maladaptive pain-related behaviors. The fourth phone call would involve asking for a commitment to practice new skills and a plan worksheet.
3. Third phase: The last 2 calls are for follow-through strategies to prevent relapse. To review the changes that have occurred since the last session, the MI-trained health care professional will praise and reinforce any and all approximations of progress. He or she will also review behavioral indicators of motivation, patient's responses to questions concerning reasons for making or maintaining changes, and barriers to adherence. He or she will again obtain a commitment to follow through on the new plan.

Duloxetine. We chose duloxetine as the first line drug because: (1) it has established efficacy for CMP and FDA approval for that indication; and (2) it is available in generic form, which makes it more readily available.

At study entry, all participants will receive duloxetine 30 mg once daily for one week. At Week 1, subjects who tolerate the 30 mg daily dose and do not have chronic kidney disease stage 3 will begin 60 mg once daily for 24 weeks. Subjects with CKD-3 tolerating 30mg daily, will continue on 30mg for 24 weeks. At week 25, participants will return to the research clinic for outcome assessments.

To assure safety of study participants, subjects will complete a symptom monitoring form (formerly labeled as medication side effects checklist) at week 1, week 2, week 4, week 13 and week 25. The subject may be contacted via text messaging as an adjunct to phone calls to assess duloxetine symptoms

monitoring at weeks 2 and 4 and for appointment reminders. The medical safety officer will be informed of any AEs (at week 1, week 2, week 4, week 13 and week 25) that require medical attention. For AEs that require medical attention, the study Medical Safety Officer will directly contact the participant to provide immediate care and guidance.

At the last study visit (week 25), participants who would like to stop the medication will be provided duloxetine 30 mg once daily for 7 days and medication treatment will then stop (tapering regimen). Subjects already taking 30 mg daily will stop dosing at their week 25 visit. Those who would like to continue duloxetine will be prescribed a 2-week supply of duloxetine and will be instructed to talk to their primary care provider (PCP). In addition, the investigator will send a Wake One message to the PCP to consider continuation of duloxetine.

Other treatments. The use of over-the-counter analgesic medications will be permitted and assessed to adjust for co-intervention differences between groups in the analyses.

6.1.2 ADMINISTRATION AND/OR DOSING

See Duloxetine dosing information under Section 6.1.1.

See MOP chapter 09, Intervention, for more details.

6.2 FIDELITY

6.2.1 INTERVENTIONIST TRAINING AND TRACKING

Health care professional-delivered MI.

To assess treatment fidelity, 10% of all audiotaped MI sessions will be reviewed. A qualified MI consultant , will use the MITI 4 method in evaluating treatment integrity⁸⁰. The MITI method represents a focused tool for evaluating competence in the use of MI.

6.3 MEASURES TO MINIMIZE BIAS: RANDOMIZATION AND BLINDING

The PI and the analysis team at the clinical site will remain blinded to group assignment throughout the study. Randomization will be stratified by number of pain sites (≤ 2 vs. ≥ 3 sites) and opioid use. Number of pain sites is included as a stratification variable, since it has been associated with worse outcomes ⁸¹⁻⁸³.

The data team , who is blinded of treatment group assignment, has the primary responsibility of analyzing outcome data throughout the study.

Randomization will be accomplished through the REDCap Randomization Module. REDCap helps implement a defined randomization model within the study project, by allowing users to 1) Define all of the randomization parameters; 2) Create and upload a custom randomization table (i.e., allocation list). The table serves as a lookup table for deciding how to randomize subjects/records. The module also monitors the overall allocation progress and assignment of randomized subjects.

For more randomization details, see MOP chapter 07, Randomization.

6.4 STUDY INTERVENTION/EXPERIMENTAL MANIPULATION ADHERENCE

Importance of Maintaining and Enhancing Treatment Outcome of Web-based CBT

As in the in-person CBT protocol, participants in a web-based CBT program are typically asked to practice each new cognitive or behavioral pain coping skills after learning it. Fundamental to the long term effectiveness of CBT is the requirement that pain coping skills are applied or practiced on a regular basis. In a study of traditional CBT for chronic pain, pre- to post-treatment changes in pain control and catastrophizing mediated the effects of CBT on pain and activity interference⁵². In fibromyalgia, treatment outcomes were most closely related to 5 coping strategies or skills: decreased guarding, increased use of exercise, seeking support from others, activity pacing, and use of coping self-statements³⁰. Unfortunately, as with face-to-face CBT programs, maintenance of clinical improvements from web-based CBT has **not** been consistently observed⁵⁰ partly due to reduced use of cognitive and behavioral pain coping skills over time.

Rini C, Keefe F et al. evaluated the effectiveness of web-based CBT (+ physiotherapist-guided home exercise delivered through Skype) to 148 persons with chronic knee pain. Improvements in pain and function with the intervention were large at 3 months (immediate post-intervention) and were greater than those in the control group³. Benefits were apparent at follow-up, although between group differences were reduced. Further, 64% of the CBT practice exercises (i.e., relaxation, coping thoughts, pleasant imagery, distraction, problem solving, activity-rest cycling, pleasant activity scheduling) were completed at 3 months with numbers decreasing during follow-up to 41%. Based on these findings, treatment strategies are needed to motivate continuous use or practice of pain coping skills to achieve long term success.

MI to Enhance Benefits of Web-based CBT

MI is an effective counseling approach to elicit behavior change (e.g., from sedentary lifestyle to physically active lifestyle, from poor food choices to healthier food choices to achieve weight loss, etc.)⁵³⁻⁵⁷. In contrast to delivering simple advice, a MI-trained health care professional helps a patient discuss the pros and cons, and the barriers and solutions to behavior change; consequently, enhancing self-efficacy. Self-efficacy determines whether an individual attempts a given task, the degree of persistence when difficulty is encountered and ultimate success or failure of the behavior.

Preliminary Data: In our RCT study⁵⁸, 216 participants with fibromyalgia were randomized to MI to increase physical activity vs. education (attention) control. Over a 12-week period, participants received either **six** telephone-delivered MI or educational (attention control) instructions. Post intervention, MI was superior to control in increasing the number of weekly hours of self-report physical activity. At follow up, more MI participants than controls exhibited meaningful improvement in global severity. Additionally, participants in the MI group had a significantly greater improvement (i.e., walked longer distance) in the 6-minute walk test compared to controls.

Given our success on the use of telephone-delivered MI, it is reasonable to hypothesize that six sessions of telephone-delivered MI to increase participant's continued practice of pain coping skills will enhance treatment outcomes.

The web-based CBT program (painTRAINER) utilizes online tools as well as a workbook to help participants track goals for completing pain coping modules and practicing coping skills, log practices, log coping confidence, and view progress.

See Table 1 in Section 1.3, Schedule of Activities, for a list of study measures and time points for data collection.

6.5 CONCOMITANT THERAPY

For this protocol, participants may use the medications that they were on at study entry including opioid and non-opioid analgesics for pain control, including over-the-counter medications and dietary supplements, and prescribed medications. Medication usage will be assessed at each IPV and documented in the relevant Case Report Form (CRF).

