5.2 EXCLUSION CRITERIA

An individual who meets any of the following criteria will be excluded from participation in this study:

1. uncontrolled hypertension - sitting systolic blood pressure >170 mmHg or diastolic blood pressure >100 mmHg at screening - (because duloxetine rarely increases blood pressure);
2. active suicidal ideation;
3. planned elective surgery during the study period (to avoid the confounding effect of possible complicated post-surgery recovery course on the primary outcome);
4. ongoing unresolved disability claims;
5. inflammatory arthritis (e.g., lupus and ankylosing spondylitis);
6. cancer-related musculoskeletal pain;
7. pregnancy;
8. history of bipolar disorder or schizophrenia;
9. narrow angle glaucoma;
10. participant reported chronic kidney disease stage 4, eGFR <30 and/or severe renal impairment (creatinine clearance <30);
11. current use of duloxetine;
12. current use of any of the following medications (to avoid adverse drug-to-drug interactions): tricyclic antidepressant > 25 mg daily dose, monoamine oxidase inhibitors, fluoxetine, sertraline, paroxetine, citalopram, escitalopram, venlafaxine, milnacipran, mirtazapine, , or aripiprazole, serotonin precursors (e.g., tryptophan), and strong CYP1A2 inhibitors (e.g., ciprofloxacin, other fluoroquinolones, fluvoxamine and verapamil);
13. poly-pharmacy (defined as concurrent daily use of 4 or more centrally acting medications for anxiety (anxiolytics), insomnia (hypnotics), anti-psychotic and anticonvulsants (gabapentin and pregabalin are permitted, if subject on a stable dose for at least 4 weeks).

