7.1 DISCONTINUATION OF STUDY INTERVENTION/EXPERIMENTAL MANIPULATION

When a subject discontinues from the study intervention but not from the study, remaining study procedures will be completed as indicated by the study protocol. If a clinically significant finding is identified (including, but not limited to changes from baseline) after enrollment, the investigator or qualified designee will determine if any change in participant management is needed. Any new clinically relevant finding will be reported as an adverse event (AE).

The data to be collected at the time of study intervention discontinuation will include the following:

- The reason(s) for discontinuing the participant from the intervention, and methods for determining the need to discontinue
- If the participant is due to complete assessments within 2 weeks of being discontinued from the study intervention, those assessments will be administered at the time of discontinuation; if the next scheduled assessments are more than 2 weeks from the discontinuation date, the discontinued participant will wait for the next scheduled assessment. Thereafter, the participant will be included in all future scheduled assessments, even though not participating in the intervention.

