7.2 PARTICIPANT DISCONTINUATION/WITHDRAWAL FROM THE STUDY

Participants are free to withdraw from participation in the study at any time upon request.

An investigator may discontinue a participant from the study for the following reasons:

- Significant study intervention non-compliance, unless varying compliance is an aspect of the study objectives
- Lost-to-follow up; unable to contact subject (see **Section 7.3, Lost to Follow-Up**)
- Any event or medical condition or situation occurs such that continued collection of follow-up study data would not be in the best interest of the participant or might require an additional treatment that would confound the interpretation of the study
- The participant meets an exclusion criterion (either newly developed or not previously recognized) that precludes further study participation

The reason for participant discontinuation or withdrawal from the study will be recorded on the Participant Status form. Subjects who sign the informed consent form and are randomized but do not receive the study intervention may be replaced. Subjects who sign the informed consent form, and are randomized and receive the study intervention, and subsequently withdraw, will not be replaced.

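### Exclusion 12 bars drugs that interact with duloxetine only at entry; no during-study rule makes starting one an automatic trigger for a decision on duloxetine

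*Combined protocol and SAP*

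**What the plan says.** Section 5.2, item 12, excludes "current use of any of the following medications (to avoid adverse drug-to-drug interactions): tricyclic antidepressant > 25 mg daily dose", followed by monoamine oxidase inhibitors, several named antidepressants, aripiprazole, serotonin precursors and "strong CYP1A2 inhibitors (e.g., ciprofloxacin, other fluoroquinolones, fluvoxamine and verapamil"). It is worded as an entry criterion.

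Under section 6.1.1, duloxetine runs for one week at 30 mg and then 24 weeks at 60 mg (30 mg in stage 3 kidney disease).

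Section 6.5 says that "participants may use the medications that they were on at study entry", and that "Medication usage will be assessed at each IPV" and entered on a case report form. It names no prohibited drugs and no action if one appears. In the co-intervention item, sections 3 and 9.4.9 both state that the trial follows medication use without limiting it.

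Four pieces of text could lead to action:

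- **Section 7.1.** After a clinically significant finding, "the investigator or qualified designee will determine if any change in participant management is needed". The next sentence has new clinically relevant findings reported as adverse events. For a participant taken off the intervention: "Thereafter, the participant will be included in all future scheduled assessments, even though not participating in the intervention".
- **Section 7.2.** "An investigator may discontinue a participant from the study for the following reasons", one of which is "The participant meets an exclusion criterion (either newly developed or not previously recognized) that precludes further study participation".
- **Section 8.2, item 4a.** Staff report adverse effects to the medical safety officer. Where medical attention is needed, that officer contacts the participant and considers adjusting or stopping the study drug.
- **Section 8.3.3.1.** The officer reviews adverse events reported at any time.

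Pregnancy, which is exclusion 7, has its own during-study rule in section 8.2, item 4c: duloxetine stops and the participant stays in the study.

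**The concern.** The protocol's own reason for exclusion 12 is interaction with the study drug. That reason does not lapse at randomization; it holds for as long as duloxetine is taken. Yet the bar is not carried into the dosing period. The section where staff would look for such a rule, 6.5, deals with what participants were already taking and with recording.

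Starting a listed drug is foreseeable. Exclusion 12 names many antidepressants, the co-intervention survey asks about psychotropic drugs received since the last follow-up, and the utilization outcomes count new psychiatry referrals for medication. A low-dose tricyclic allowed at entry could also be raised above 25 mg.

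What is at stake is participant safety: avoidable combined exposure with no required decision about duloxetine. The primary comparison is not at issue. Section 9.4.2 analyses participants as randomized and plans a sensitivity analysis for new pain-related medication.

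**Working it through.** The plan states no figure to reproduce. The check compares the text with a specific event and adds a short calculation on the visit schedule.

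**1. Exposure.** 1 + 24 = 25 weeks on duloxetine (section 6.1.1).

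**2. Scheduled medication review.** Table 1 gives in-person visits at weeks 0, 1, 13 and 25, and 6.5 attaches the review to each. The gaps are 1, 12 and 12 weeks, so the longest wait is 12 weeks. If starts are spread evenly over weeks 1 to 25 (an assumption), the mean wait to the next review is the sum of squared gaps over twice their total: (144 + 144) / (2 × 24) = 6.0 weeks. Including the first week of dosing gives (1 + 144 + 144) / (2 × 25) = 5.8 weeks. These are waits to a scheduled review; a participant may report earlier. Table 1 as extracted shows no week 1 tick for the non-study medication list. If week 1 were not a review, the first gap would be 13 − 0 = 13 weeks.

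**3. Test case.** A primary care provider starts sertraline, which exclusion 12 names, at week 5. The participant has no symptoms.

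- *6.5:* the drug is recorded at week 13. No action is attached.
- *Sections 3 and 9.4.9:* medication use is not limited, and exclusion-12 drugs are not exempted.
- *7.1:* a decision follows if someone judges the new drug a clinically significant finding. If it is judged clinically relevant, it becomes an adverse event and so reaches the medical safety officer. The trigger is that judgement, not the start of the drug.
- *8.2, item 4a:* the study-drug decision follows adverse effects needing medical attention. Here there are none.
- *8.3.3.1:* the officer reviews adverse events reported. An uneventful new prescription is not plainly one, although the illness behind it may be.
- *7.2:* this is the only text that names a newly met exclusion criterion. It is permissive, it applies where the criterion precludes further participation, and it acts on study participation, not on duloxetine.

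Two investigators could both follow this text, one referring the case at once and the other only recording it.

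**4. Comparison with pregnancy.** Exclusion 7 is not left to 7.1 or 7.2: it has a named event, a stated action on duloxetine, and continued participation. Exclusion 12 has no counterpart.

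**5. What a form question would do.** The Symptom Monitoring Form is given at weeks 1, 2, 4, 13 and 25, so the gaps are 1, 2, 9 and 12. On the same assumption the mean wait is (1 + 4 + 81 + 144) / (2 × 24) = 230 / 48 = 4.8 weeks. The longest wait remains 12 weeks, so a question alone is not enough and participants also need to be told to report new prescriptions.

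**The case against.** The best reply is that the protocol already routes the event. A newly found interacting drug that is judged clinically relevant becomes an adverse event under 7.1 and goes to the medical safety officer under 8.2 and 8.3.3.1. The illness behind the prescription will often be an adverse event in its own right. Table 1 provides as-needed phone contact for side effects and lists a medication modification form. Most of this stands, and it limits the point: what is missing is an automatic trigger, not any route at all.

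It is also fair that 6.5 permits only entry medications, so it never authorises an exclusion-12 drug, and that the sentence in sections 3 and 9.4.9 describes an exploratory measure. But 6.5 states no consequence, and that sentence makes no exception. The pregnancy comparison is imperfect, since pregnancy is a fixed stop and an interacting drug calls for judgement. It shows only that the protocol can tie a newly met criterion to a duloxetine decision while keeping the participant.

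Manual of procedures chapters 09 and 12 and the consent form are not available here and may hold instructions. The point therefore concerns the protocol text alone.

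Three stronger readings are not supported:

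- **Withdrawal follows, with loss of pain data.** Section 7.2 says the investigator may withdraw a participant, and only for a criterion that precludes participation. Withdrawal at week 13 would forgo the week 25 Brief Pain Inventory, but that is possible, not presumed.
- **Most short courses, such as fluoroquinolones, would pass unseen.** The documents give neither course lengths nor a start rate, so no share or count can be offered as evidence of size.
- **The primary comparison is biased.** Nothing in the documents shows this.

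**Conclusion.** The point holds as a gap in the protocol text. Exclusion 12 is confined to entry, its reason lasts for all 25 weeks of dosing, and no during-study provision makes a new listed drug, or a tricyclic raised above 25 mg, an automatic trigger for a decision on duloxetine. Scheduled medication reviews are up to 12 weeks apart.

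Severity is low to modest. General adverse-event and management routes exist, and a careful investigator would probably use them. The 12-week figure rests on Table 1 and 6.5; the mean waits also assume evenly spread starts and no reporting between visits. The number of participants affected is unknown. The case for acting is that the safety gain is specific and the change is cheap.

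**What to change.** 1. **Section 6.5.** State that exclusion-12 drugs should not be started, nor a tricyclic raised above 25 mg daily, while on study duloxetine. If this happens, the medical safety officer is notified promptly and decides, case by case, whether to taper or stop duloxetine or have the other drug changed. Brief Pain Inventory follow-up continues under 7.1.
2. **Sections 3 and 9.4.9.** Exempt exclusion-12 drugs from the sentence saying that medication use is not limited.
3. **Unless already in the manual of procedures or consent form.** Add one question on new or changed medication to the Symptom Monitoring Form, and an enrolment instruction to report new prescriptions and dose changes. Both should be the same in all arms, so they should not be placed in the motivational interviewing calls, which only one arm receives.

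The cost is an amendment to 6.5 and to one sentence that appears twice, plus at most one form item and one line of instruction. No visits are added. The downside is some extra alerts to the medical safety officer; the number cannot be estimated without a start rate.
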